2 SUMMARY OF CLINICAL EXPERIENCE

ANKON Medical Technologies, the Chinese company sister of AnX Robotica, sold about 300,000 NaviCam Capsules between 2016 to 2018. Additionally, the NaviCam Controllable System had been the subject of several articles published in scientific journals summarizing the results of clinical studies as well as real-life experience.

The Chinese FDA study was conducted to evaluate the clinical effectiveness of the NaviCam Stomach Capsule (MCC). The primary objective of the study was to compare NaviCam Stomach Capsule procedure with EGD in subjects diagnosed with gastro duodenal lesions.

The study was conducted in two centers in China all patients underwent the NaviCam Stomach Capsule procedure, followed by conventional EGD without sedation. The sensitivity, specificity, positive predictive value, and negative predictive value of detection of gastric focal lesions by MCC

were calculated, using EGD as the gold standard. One hundred subjects were enrolled in the study, but one subject refused to undergo EGD, therefore the statistical analysis was done on 99 subjects.

No adverse events were reported for any of the patients in this study. With respect to performance, the NaviCam Stomach Capsule was found to be equivalent to the EGD gold standard. All capsules were successfully expelled rectally with an average passage time of 76.1 hours.

The primary objective of the second comparative study was to compare a procedure with the MCC with gastroscopy for subjects diagnosed with gastric focal lesions. The study was conducted in 7 centers in China in which all patients underwent an MCC procedure followed by conventional gastroscopy 2 hours later without sedation. The sensitivity, specificity, positive predictive value, and negative predictive value of detection of gastric focal lesions by the MCC were calculated, using gastroscopy as the gold standard. A total of 353 subjects were enrolled in the study, but three subjects refused to undergo gastroscopy, therefore the statistical analysis was done on 350 subjects.

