4.2 Study Endpoints

Primary

Effectiveness:

For both MCC, MCC-T and EGD, rates of diagnosis of clinically relevant pathology in patients with upper abdominal pain will be assessed. Detection of D2 findings will be considered positive. Sensitivity, specificity, positive predictive value, and negative predictive values will be calculated for both MCC and EGD. In this study the “gold standard” will be the expert group’s decision regarding the presence of an abnormal finding. McNemar’s test will be used to assess for statistically significant differences between the two modalities. Sub-analyses will be performed to compare accuracies of the two modalities based on anatomic region (i.e. esophagus, stomach, duodenum) and across various lesions (i.e. ulcers, gastropathy, esophagitis, etc.).

Safety: Rate of device or procedure related adverse events during the procedures or in the follow-up period (24 hrs. post procedure).

Secondary

Examination completion: Compare rates of complete examination of the foregut by MCC or MCC-T and EGD in patients presenting with upper abdominal complaints using sets of predetermined still images

Patient Satisfaction: Assess patient satisfaction for patients undergoing MCC or MCC-T and EGD.

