5.3 Study Duration

Total duration of the study for each patient will be 7 days (+7 days) including follow-up 24-72 hrs. after the final study related procedure.

Total anticipated study duration, including data analysis and final report, is estimated to be up to 12 months.

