6.4 Visit 1 – Screening and Enrolment

Patients found to be potential study candidate will be flagged and contacted by a study nurse before their visit. The study coordinator will review the study with the patient. If patients show interest in being involved in the study, a visit will be arranged at which consent will be obtained and a PCR and symptom survey will be performed. If negative, a time and date for the MCC and EGD procedures will be arranged.

The MCC or MCC-T will be performed first followed by an EGD at least 2-3 hours later, but up to 7 days later.

A member of study staff will then extract all relevant demographic data from the patients' medical record to the patient CRF. Relevant demographic data includes but is not limited to date of birth, height, weight, gender, race, past medical history, past surgical history, medications and allergies.

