8 PATIENT BENEFIT AND RISKS

A risk management according to ISO 14971, has been conducted and is periodically reviewed. The risk management report is documented in NaviCam Capsule Endoscope System with NaviCam Stomach Capsule Risk Management Report (RM-NCES-ST-02). Risks have been proven minimized or eliminated through appropriate design control, confirmed by pre-clinical bench, laboratory, animal and clinical testing.

The NaviCam Stomach Capsule is MR unsafe. MRI exams should be avoided until capsule passage is confirmed.

Based on the available clinical data previously collected, the following anticipated adverse events may occur:

- Bloating
- Nausea
- Vomiting
- Headache
- Throat irritation
- Transient, two weeks retention of the capsule in the G.I. tract.

The main risk associated with the EGD procedure is perforation. Additionally, reaction to sedation may include:

- Difficulty breathing or an inability to breathe
- Low blood pressure
- Slow heartbeat
- Excessive sweating

Laryngeal spasm

Study Rationale

The safety and effectiveness of the NaviCam Stomach capsule has already been demonstrated via two clinical studies as well as in ongoing use in China and the EU. Basic usability and safety of the tether device was assessed by the company in healthy volunteers. The ability to visualize the esophagus utilizing the tether device may result in a simpler procedure that does not require sedation (when compared to EGD).

This study is designed to evaluate the safety and effectiveness of the NaviCam Stomach Capsule with Tether device for its intended use by comparing the obtained findings with those obtained via standard EGD.

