9 ADVERSE EVENTS

9.1 Definition

Adverse Event (AE): Any untoward medical occurrence in a subject whether device related or not.

Serious Adverse Event (SAE): adverse event that

- a) led to death,
- b) led to serious deterioration in the health of the subject, that either resulted in:
 - 1) a life-threatening illness or injury, or
 - 2) a permanent impairment of a body structure or a body function, or
 - 3) in-patient or prolonged hospitalization, or
 - 4) medical or surgical intervention to prevent life-threatening illness or injury or permanent impairment to a body structure or a body function,
- c) led to fetal distress, fetal death or a congenital abnormality or birth defect

NOTE Planned hospitalization for a pre-existing condition, or a procedure required by the CIP, without serious deterioration in health, is not considered a serious adverse event.

Serious Adverse Device Effect (SADE): Adverse Event caused by or involving the device that has resulted in any of the consequences characteristics of a Serious Adverse Event. A SADE may occur at any time after exposure to the study device.

Unanticipated Adverse Device Effect (UADE): Any serious adverse effect on health or safety or any life-threatening problem or death caused by, or associated with, a device, if that effect, problem, or death was not previously identified in nature, severity, or degree of incidence in the investigational

plan or application (including a supplementary plan or application), or any other unanticipated serious problem associated with a device that relates to the rights, safety, or welfare of subjects.

All adverse events will be graded for severity as follows:

Mild: Sign or symptom, usually transient, requiring no special treatment and generally not interfering with usual activities.

Moderate: Sign or symptom, which may be ameliorated by simple therapeutic measures; yet, may interfere with usual activity.

Severe: Sign or symptom that are intense or debilitating and that interfere with usual activities. Recovery is usually aided by therapeutic measures.

The relationship of the adverse event to the investigational device use is defined as follows:

Probably related: Follows a reasonable temporal sequence from study device delivery/retrieval and cannot be reasonably explained by known characteristics of the subject's clinical data.

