10.4 Safety Analysis

Analysis for the safety endpoint will be descriptive in nature.

AEs will be coded by the MedDRA (version 18.0 or later) system organ class and preferred term. AE data will be listed individually and summarized by system organ class and preferred terms within a system organ class for each indication. In addition, summary of AEs will be presented by severity and relation to study treatment.

Serious adverse events will be similarly summarized.

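### Safety follow-up ends before the listed two-week capsule retention can be ascertained, and the capsule-versus-EGD safety comparison has no EGD attribution rule or by-procedure table

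*Combined protocol and SAP*

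**What the plan says.** **Follow-up.** The safety endpoint in Section 4.2 is "Safety: Rate of device or procedure related adverse events during the procedures or in the follow-up period (24 hrs. post procedure", and the synopsis repeats it. The text does not say which procedure starts the clock. The synopsis (Study Duration) and Section 6.6 count 24 h from the last procedure, and the Section 6.6 contact is also the termination visit. Section 5.3 gives a patient duration of "7 days (+7 days) including follow-up 24-72 hrs. after the final study related procedure".

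**Order of procedures.** Section 6.4: "The MCC or MCC-T will be performed first followed by an EGD at least 2-3 hours later, but up to 7 days later".

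**Passage and retention.** Section 2 reports for the earlier 99-subject study: "All capsules were successfully expelled rectally with an average passage time of 76.1 hours". Section 8 includes among the anticipated adverse events: "Transient, two weeks retention of the capsule in the G.I. tract". It also ties MRI to confirmed capsule passage. The table in Section 6.2 has no row for passage.

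**Attribution and tabulation.** The second primary objective (synopsis and Section 4.1) compares capsule safety with EGD. Section 9.1 introduces its categories with "The relationship of the adverse event to the investigational device use is defined as follows", and its lowest category is defined by the absence of a relationship to the study device. Section 9.2 mentions the investigational procedure but gives no scale. Section 10.4 is descriptive: "AE data will be listed individually and summarized by system organ class and preferred terms within a system organ class for each indication". It adds summaries by severity and by relation to study treatment.

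**The concern.** Retention is a device-specific event that the protocol itself anticipates, yet the last scheduled contact comes before that event could be complete. Because passage is not recorded, a patient leaving the study with a capsule in normal transit cannot be told apart from one whose capsule is retained. The earlier study could state that all capsules were expelled; this trial, as scheduled, could not.

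The second issue is the comparison. Safety against EGD is a primary objective, but the only graded relatedness scale has no place for EGD or sedation. If the plan is followed literally, an EGD complication is filed as unrelated and appears in no EGD-specific row. Readers of the final report would then have no prespecified EGD rate to set beside the capsule rate.

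**Working it through.** **What can be reproduced.** The mean passage time of 76.1 h is an observed mean with no SD, median or range, so it cannot be recomputed. The one checkable safety figure in Section 2 agrees: 5/350 = 1.43%, printed as 1.4%. The plan gives no power, margin or test for safety.

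**Observation time after ingestion.** Inputs: capsule-to-EGD gap 2-3 h up to 7 × 24 = 168 h (Section 6.4); last contact 24 h after the final procedure (Section 6.6), or up to 72 h (Section 5.3); retention 14 × 24 = 336 h (Section 8). Observation = gap + follow-up.

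| Gap to EGD | Follow-up after EGD | Observation from ingestion | Short of 336 h by |
|---|---|---|---|
| 2 h | 24 h | 26 h | 310 h |
| 3 h | 24 h | 27 h | 309 h |
| 2 h | 72 h | 74 h | 262 h |
| 3 h | 72 h | 75 h | 261 h |
| 168 h | 24 h | 192 h | 144 h |
| 168 h | 72 h | 240 h | 96 h |

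No combination reaches 336 h. If the endpoint clock runs separately from each procedure, the capsule window is only 24 h and the shortfall is 312 h.

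**Passage status at the call.** This step needs an assumption, because the spread of transit times is not given. With log-normal or gamma times, mean 76.1 h and an assumed coefficient of variation of 0.3 to 1.0, the share of capsules not yet passed is 71% to more than 99% at 26 h, 35-50% at 74 h, at most about 8% at 192 h and at most about 4% at 240 h. These are capsules in ordinary transit, not adverse events. They show only that a passage question at a same-day call would be uninformative.

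**Overlap.** With same-day EGD, the 24 h after the capsule and the 24 h after EGD share 24 − 3 = 21 h to 24 − 2 = 22 h. Timing alone therefore cannot assign most events, and the relatedness field has to.

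**Attribution, side by side.** The endpoint counts device- or procedure-related events. The scale in Section 9.1 grades only the device. Section 10.4 groups by indication and by relation to study treatment. An EGD event therefore meets the endpoint wording but has no category to be recorded in and no table row.

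**Precision.** With n = 70 (Section 10.6) and zero events, the two-sided 95% upper limit is 1 − 0.025^(1/70) = 5.1%. At a true rate of 1%, the chance of seeing at least one event is 1 − 0.99^70 = 51%.

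**The case against.** Several stronger readings are tempting, and the documents do not support them.

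- *Events are attributed only to the capsule.* This is true of the categories in Section 9.1, but the endpoint itself includes procedure-related events.
- *The comparison with EGD cannot be made.* Section 6.2 schedules adverse event evaluation at the capsule visit, the EGD visit and the call. Items 7-10 of the Appendix I questionnaire ask about problems during and after each test separately. Section 8 also lists partly distinct events for the capsule and for sedation. A crude descriptive comparison is available.
- *A zero retention rate is guaranteed.* When EGD falls on day 7, the call comes at 192 h or later, and item 8 asks about capsule problems after the test. Section 9.1 lets a serious device effect count at any time after exposure. A symptomatic retention could therefore surface.
- *Most capsules would be missed events.* The percentages not yet passed describe normal transit under assumed distributions, and the 76.1 h sentence itself says that all capsules were expelled. The relevant comparator is 336 h.
- *Observation time is proven unequal between modalities.* Counted from the last procedure it is unequal. If the clock starts at each procedure, the windows are equal. The text is ambiguous.

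Two further cautions stand. The flow diagram and the appended timeline are not in the available text, so the absence of a passage check is shown for the table and the written visit descriptions only. And in a pilot of this size, even complete ascertainment is imprecise. None of this supplies a contact at two weeks, a passage record or an EGD relatedness category.

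**Conclusion.** The point holds in this form. Scheduled observation ends 26-192 h after ingestion, or at most 240 h, against 336 h for the retention event that Section 8 lists; the shortfall is 96-310 h when counted from the last procedure. Two-week retention therefore cannot be ascertained under any permitted schedule. Separately, the primary safety comparison with EGD has neither an attribution rule for EGD or sedation nor a by-procedure table. It is underspecified rather than impossible.

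The shortfall rests only on times stated in the protocol. The transit percentages depend on an assumed distribution and on transit resembling the earlier study, and the conclusion does not need them. The precision figure uses the 70 patients of Section 10.6; the synopsis says 100, for which the zero-event limit would be 1 − 0.025^(1/100) = 3.6%.

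**What to change.** 1. Reconcile the follow-up statements in the synopsis (Study Duration and Study Endpoints) and Sections 4.2, 5.3 and 6.6, and state which procedure starts the clock.
2. Record capsule passage (yes/no/date, by patient report) and late capsule events in one data-collection call timed at 14 days from ingestion. Report retention separately from the 24 h rate. Time the call from ingestion because, if the 7 (+7)-day patient window starts at Visit 1, it closes before 336 h after ingestion.
3. Record the onset time of each adverse event, and add relatedness fields for EGD/sedation and for gastric preparation beside the device. Preparation needs its own field because Section 2 attributes events to it in 4 of the 5 affected patients.
4. In Section 10.4, replace tabulation by indication with tabulation by procedure (MCC, MCC-T, EGD), using a 24 h window after each procedure. Assign same-day overlapping events by the relatedness fields and flag them. Do not cut capsule events off at the start of EGD, since that would leave the capsule only 2-3 h against 24 h for EGD.

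The cost is one call, which may fall slightly beyond the current patient window, a few CRF fields and revised table shells. The reported rates may be less favourable, and the retention estimate will remain imprecise.

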4 STUDY OBJECTIVES

4.1 Study Objectives

Primary:

1. To demonstrate the effectiveness of the MCC and MCC-T when compared to EGD in identifying esophageal, gastric and duodenal abnormalities in patients presenting with upper abdominal symptoms.
2. To evaluate rates of adverse events and overall safety of MCC-T as compared to EGD.

Secondary:

1. To compare rates of complete examination of the foregut by MCC, MCC-T and EGD in patients presenting with upper abdominal complaints using sets of predetermined still images
2. To assess patient satisfaction for patients undergoing MCC, MCC-T and EGD.

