Once the final images have been obtained the capsule will be piloted through the pylorus and into the duodenum. Following a brief examination (with photo documentation) of the duodenal bulb the capsule will be released into the small intestine with the video still running. Once the capsule reaches the distal duodenum the video recording can then stop, and the examination is completed.

Recording of MCC procedure:

The responsible study staff member will generate a procedure report documenting his/her findings that will then be cosigned by the study staff attending. This document will be deidentified and only linked to the patient by their study ID number. The document will be placed in the patient's study file along with the video recording of the entire procedure. The patient must be blinded to the findings at this time.

EGD Procedure:

At least two hours after the MCC-T ingestion the subject will be brought to the endoscopy procedure area; study staff will confirm that the patient has been NPO for at least 2 hours after the ingestion of water for the MCC or MCC-T procedure. If practicable, both procedures may be performed on the same day. If not, the EGD will be performed within 7 days and the patient will need to fast overnight prior to the EGD appointment and have nothing by mouth for at least 2 hours prior to arrival (per standard EGD instructions).

The patient will then be sedated using conscious sedation with midazolam and fentanyl or monitored anesthesia with propofol. The upper endoscopy will be performed in the left lateral position. The same photos of the esophagus, stomach, and duodenum will be obtained as described above. The doctor performing the upper endoscopy will not have any knowledge of the findings of the MCC procedure. The patient is then allowed to recover for 30 minutes in the recovery room and discharged.

Image management

Images from the MCC-T procedure will be stored in the Navicam system.

Images of the endoscopic procedure will be stored in Provation and EPIC as per routine.

Images from the MCC, MCC-T and EGD will be printed on photographic paper for comparison by the study team.

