6.6 Visit 4 – Telephone Follow-up and Termination

24 hours after all procedures are completed the study coordinator will call the patient and briefly go through a standardized form of questions. Most importantly, the study coordinator will ask the patient which procedure they preferred and would be more agreeable to having done again (Questionnaire provided in Appendix I).

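### The primary capsule-versus-EGD safety comparison has no adverse-event table by procedure and no rule for events that follow both, although sedated EGD may start 2-3 hours after the capsule

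*Combined protocol and SAP*

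**What the plan says.** The safety comparison is a primary objective. Section 4.1 states it as "To evaluate rates of adverse events and overall safety of MCC-T as compared to EGD"; the synopsis states it for both MCC and MCC-T. The endpoint in 4.2 is the "Rate of device or procedure related adverse events during the procedures or in the follow-up period (24 hrs. post procedure" interval. It does not say which procedure starts the clock, or to which procedure an event belongs when it follows both.

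On order and spacing, section 6.4 says "The MCC or MCC-T will be performed first followed by an EGD at least 2-3 hours later, but up to 7 days later". Section 6.5 counts from ingestion ("At least two hours after the MCC-T ingestion the subject will be brought to the endoscopy procedure area") and adds "If practicable, both procedures may be performed on the same day", with EGD otherwise within 7 days. On sedation it says "The patient will then be sedated using conscious sedation with midazolam and fentanyl or monitored anesthesia with propofol".

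Follow-up is described in three ways. Section 4.2 gives 24 hours after the procedure. The synopsis and 6.6 give 24 hours after the last procedure, 6.6 in the words "24 hours after all procedures are completed the study coordinator will call the patient". Section 5.3 gives 24 to 72 hours after the last one.

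Section 10.4 makes the analysis descriptive. Events are listed individually, "summarized by system organ class and preferred terms within a system organ class for each indication", and also summarised by severity and by relation to study treatment. Section 9.1 defines that relation against the investigational device. The schedule in 6.2 places adverse-event evaluations at Visits 2, 3 and 4, without timing the Visit 3 evaluation relative to sedation.

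**The concern.** A comparison of two procedures needs a count for each. Here every patient in the safety population has both, in a fixed order and possibly hours apart, and section 10.4 does not ask for the two counts. The capsule events anticipated in section 8 (bloating, nausea, vomiting, headache, throat irritation) are non-specific. If nausea starts some hours after both procedures, timing alone cannot assign it, and the relatedness scale has no place for EGD or its sedation.

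At stake is the numerator of a primary endpoint. Events could be charged to the capsule, to EGD, to both or to neither, depending on the assessor. With few events expected, a single allocation matters. If onset times are not collected prospectively, they cannot be reliably recovered later.

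**Working it through.** The plan gives no overlap figure and no safety margin, test or power, so there is no stated number to reproduce. The check has two parts.

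**1. How much of a capsule window lies after EGD has begun.**

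Inputs: window length W = 24 h (4.2); gap g from capsule to EGD, at least 2-3 h and at most 7 days (6.4, 6.5). Assumption: the window is counted from the capsule and g is measured from the same point.

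Share after EGD start = max(0, W − g) / W.

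| Gap g | Calculation | Share after EGD start |
|---|---|---|
| 2 h | 22/24 | 91.7% |
| 3 h | 21/24 | 87.5% |
| 4 h | 20/24 | 83.3% |
| 6 h | 18/24 | 75.0% |
| 8 h | 16/24 | 66.7% |
| 24 h or more | 0/24 | 0% |

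Sensitivity to the definition of the window:

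- Clock started at the end of the capsule examination, assumed to last 0.5-1 h, with EGD 2-3 h after ingestion: from (24 − 2.5)/24 = 89.6% to (24 − 1)/24 = 95.8%.
- Upper limit of 72 h from section 5.3, applied from the capsule: 69/72 = 95.8% at 3 h and 70/72 = 97.2% at 2 h.
- Follow-up anchored to the last procedure, as in the synopsis, 5.3 and 6.6: EGD is always last, so the whole post-procedure follow-up comes after both procedures, whatever the gap. This reading provides no separate capsule follow-up.

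The overlap is mutual. If each 24 h window starts with its own procedure, the two share 24 − g hours, so at g = 2-3 h the same 88-92% of the EGD window lies inside the capsule window.

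**2. Whether the plan can separate events in the overlap.**

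- By table: 10.4 specifies organ class, preferred term, indication, severity and relation to study treatment. Neither procedure nor same-day versus later EGD is a table dimension.
- By causality: the categories in 9.1 refer to the investigational device. The only alternative cause named under possible relation is the subject's own clinical state. In 9.2 the investigator assesses the involvement of the investigational procedure. EGD and sedation appear in neither, although the endpoint's wording could admit EGD-related events.
- By timing: neither 4.2 nor 10.4 classifies onset as before or after EGD, and the Visit 3 evaluation may fall before or after sedation.
- By patient report: Appendix I, items 7-10, asks separately about problems at the time of and after each test. The answers are free text, ask for no onset time, and are collected in the single call after all procedures.

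**Scale.** With the 70 patients of section 10.6, moving one patient's event changes a procedure's rate by 1/70 = 1.4 percentage points. With the 100 patients in the synopsis it is 1/100 = 1.0 point. If 70 patients were split equally between MCC and MCC-T (an assumption), it is 1/35 = 2.9 points per capsule type.

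**The case against.** The strongest reply is that the plan already attributes events. The endpoint is restricted to events related to the device or procedure, 10.4 summarises relation to study treatment, the investigator assesses involvement, all events are listed, and the questionnaire asks about each test separately. This stands to the following extent: a reader might infer that the plan counts EGD and sedation effects as capsule events, and the documents do not say so. They only lack a rule to prevent it. The reply does not close the gap, because the attribution scale has no entry for EGD or sedation.

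Other tempting readings also fail:

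- That 88-92% describes same-day EGD in general. The 2-3 h gap is a minimum, and the expected same-day share is not given.
- That the capsule has its own defined 24-hour window. This is a natural reading of 4.2, but other sections anchor follow-up to the last procedure.
- That contamination runs only towards the capsule. Every EGD follows a capsule, and section 2 reports a mean passage time of 76.1 hours in the two-centre study, so late capsule effects can enter the EGD count.
- That the 1.4% rate in section 2 (5 of 350) is a clean capsule rate to which assumed EGD symptom rates can be added. In that study gastroscopy, without sedation, followed the capsule by 2 hours, so it had the same overlap.
- That a test or error rate is damaged. The analysis is descriptive, so none is affected.

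**Conclusion.** The concern holds as a gap in definition and tabulation. Followed as written, the plan produces no adverse-event table by procedure for a primary objective that compares procedures. It grades relatedness to only one of them and has no rule for events that follow both. The exposed share of a capsule-anchored 24-hour window is at most 88-92% when EGD follows at the minimum 2-3 hours from the start of that window, is two-thirds or more for gaps up to 8 hours, and is nil at 24 hours or more. These figures rest on counting from the capsule, which 4.2 suggests but does not state. How many patients are affected depends on the same-day share, which is unknown.

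The bias could go either way, and its size cannot be estimated from the documents. A descriptive rate still needs a defined numerator, and at this sample size one reallocated event moves a rate by 1.0-1.4 points. The plan should be changed before data collection; the gap does not invalidate the study.

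**What to change.** - In 10.4, replace the breakdown by indication with one by procedure (MCC, MCC-T, EGD). Align the safety population in 10.2, which names only the capsule with tether, so that MCC patients enter the table.
- Add an onset date and time to the adverse-event CRF, and classify each event as before or after the start of EGD sedation.
- Time the adverse-event evaluation already scheduled at Visit 3 before sedation, so that events in the capsule-only interval are captured.
- Extend the relatedness assessment in 9.1 to capsule, EGD/sedation, or both/indeterminate.
- Report events that follow both procedures separately, split by same-day and later EGD.
- State in 4.2 which procedure starts the clock, and reconcile the 24 hours of the synopsis, 4.2 and 6.6 with the 24 to 72 hours of 5.3.

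A head-to-head comparison over equal-length windows is not recommended. In same-day patients it would cut the capsule period to the few hours before EGD and discard events from an already small count.

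The cost is one CRF field, one attribution item, the ordering of an existing evaluation, and changes of wording. No visit, procedure or sample size changes. The downside is that some events will be reported as not attributable to a single procedure.
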